5.3 Agent Administration

In general, there is a +/- 3 day window for lenalidomide administration to allow for scheduling related issues.

Lenalidomide

Celgene Corporation will supply lenalidomide to study participants at no charge through Celgene's Revlimid Risk Evaluation and Mitigation Strategy[™] (REMS) (formerly known as RevAssist® Program). Lenalidomide will be supplied as capsules for oral administration and will be taken on days 1-21 of a 28 day cycle. The first cycle will be dosed at 10 mg with a dose escalation to 25 mg at cycle 2 in the absence of toxicity. If the creatinine clearance is 30 to \leq 60 then the starting dose will be still be 10 mg at cycle 2. In the absence of grade 3 or greater toxicity during cycle 1 the dose will stay at 10 mg during cycle 2 in this patient population. In the absence of grade 3 or greater toxicity at the week 8 assessment the dose can be escalated to 25 mg daily on days 1-21 of a 28 day cycle in patients whose baseline CrCl was 30 to \leq 60 and in whom CrCl subsequently improves to >60. No dose escalation if permitted after week 8. The maximum number of cycles is 12 inclusive of the dose escalation cycle(s). Lenalidomide will be taken at approximately the same time every day (+/-2 hours) and there are no dietary considerations. Vomited doses will not be made-up. Missed or forgotten doses can be made up if taken within twelve hours of the scheduled administration on the same calendar day. For example, if the patient is scheduled to take lenalidomide at 8 AM a missed dose can be made up prior to 8 PM on the day of treatment. However, if the patient was scheduled to take a dose at 4 PM and that dose is missed, the dose must be taken before midnight of the same calendar day. If

these conditions cannot be fulfilled the dose should be skipped.

Packaging

Lenalidomide will be shipped directly to patients from a specialty pharmacy. Bottles will contain a sufficient number of capsules for one cycle of dosing. Lenalidomide supplies are dispensed in individual bottles of capsules. Each bottle will identify the contents as study medication. In addition, the label will bear Celgene's name, quantity contained and the standard caution statement as follows: "Caution: New drug - Limited by Federal law to investigational use." The study drug label must be clearly visible. Additional labels must not cover the Celgene label.

Return

Patients should return all unused study medication to the study site at each applicable study visit.

Accountability The disposition of all Lenalidomide study drug should be documented from the time of receipt at the site through patient dispensing and return.

The Investigator and/or the responsible site personnel must maintain accurate records of the receipt of all study drug shipped by Celgene Corporation or its designee. Study drug accountability records must also be maintained that include the patient number to whom the study drug was dispensed, the date and quantity of the study drug dispensed.

The study drug supply should be retrieved from patients at the end of each dosing cycle. The quantity of study drug and the date returned by the patient should be recorded in the study drug accountability records.

Remaining unused study drug supply will be destroyed at the clinical site, standard institutional policy should be followed. Records documenting the date of study drug destruction, relevant lot numbers, and destroyed should be maintained,

Storage

Lenalidomide should be stored at room temperature away from direct sunlight and protected from excessive heat and cold.

Unused study drug supplies

Patients will be instructed to return empty bottles or unused capsules to the clinic site. Celgene will instruct the Investigator (or designee) on the return or destruction of unused study drug. If any study drug is lost or damaged, its disposition should be documented in the source documents. Study drug supplies will be retained at the clinical site pending instructions for disposition by Celgene.

Lenalidomide should not be handled by females of child-bearing potential unless wearing gloves.

- 5.3.1 CTEP and/or CIP IND Agent(s), or other IND agent N/A
- 5.3.2 Other Agent(s): N/A
- 5.3.3 Other Modality(ies) or Procedures

N/A

5.4 General Concomitant Medication and Supportive Care Guidelines

Anti-emetics will be prescribed per physician and patient preference with the exception that steroids should not be utilized as an anti-emetic. If patients require glucocorticoids for any reason during treatment they should be removed from the protocol unless the expected duration of treatment is less than 7 days and the glucocorticoids will not be given on a recurring basis. Erythroid growth factors are not permitted on protocol due to concerns about augmenting clotting risk. Filgrastim and pegfilgrastim are not permitted during cycle 1 but are permitted during the second and subsequent cycles as outlined in section 6 on dose modification (note, filgrastim and pegfilgrastim are not allowed during the first 8 weeks in patients with a CrCl of 30 to ≤ 60).

Because there is a potential for interaction of lenalidomide with other concomitantly administered drugs through the cytochrome P450 system, the case report form must capture the concurrent use of all other drugs, over-the-counter medications, or alternative therapies.

Lenalidomide is known to increase the risk of arterial and venous thrombosis. Patients not already on systemic anticoagulation (warfarin, low molecular weight heparin, or equivalent) for other medical reasons are required to take aspirin 81 mg daily for the duration of the study.

5.5 Criteria for Taking a Participant Off Protocol Therapy

Duration of therapy will depend on individual response, evidence of disease progression and tolerance. In the absence of treatment delays due to adverse event(s), treatment may continue for 12 cycles or until one of the following criteria applies:

- Disease progression
- Intercurrent illness that prevents further administration of treatment
- Unacceptable adverse event(s)
- Participant demonstrates an inability or unwillingness to comply with the oral medication regimen and/or documentation requirements

- Participant decides to withdraw from the protocol therapy
- General or specific changes in the participant's condition render the participant unacceptable for further treatment in the judgment of the treating investigator
- Recurrent toxicity (see section 6)
- Patient becomes pregnant or cannot comply with birth control requirements.

Participants will be removed from the protocol therapy when any of these criteria apply. The reason for removal from protocol therapy, and the date the participant was removed, must be documented in the case report form (CRF). Alternative care options will be discussed with the participant.

A QACT Treatment Ended/Off Study Form will be filled out when a participant is removed from protocol therapy. This form can be found on the QACT website or obtained from the QACT registration staff.

In the event of unusual or life-threatening complications, treating investigators must immediately notify the Overall PI, [name] at [contact] or [contact] ([name]).

5.6 **Duration of Follow Up**

Participants will be followed for 3 years from the initiation of treatment, until subsequent therapy or until removal from study or death, whichever occurs first. Participants removed from protocol therapy for unacceptable adverse event(s) will be followed until resolution or stabilization of the adverse event.

5.7 Criteria for Taking a Participant Off Study

Participants will be removed from study when any of the following criteria apply:

- Lost to follow-up
- Withdrawal of consent for data submission
- Initiation of subsequent therapy
- Death
- Completion of all study procedures

The reason for taking a participant off study, and the date the participant was removed, must be documented in the case report form (CRF).

A QACT Treatment Ended/Off Study Form will be filled out when a participant comes off study. This form can be found on the QACT website or obtained from the QACT registration staff.

6. DOSING DELAYS/DOSE MODIFICATIONS

Dose delays and modifications will be made as indicated in the following table(s). The descriptions and grading scales found in the revised NCI Common Terminology Criteria for Adverse Events (CTCAE) version 4.03 will be utilized for dose delays and dose modifications and version 3.0 should be used for tumor flare. A copy of the CTCAE version 4.0 can be downloaded from the CTEP website

http://ctep.cancer.gov/protocolDevelopment/electronic applications/ctc.htm.

Note that tumor flare reaction is managed differently from other AEs as outlined in Table 4. Lenalidomide should be held for any grade 3 or higher toxicity except in the incidence of a blistering skin rash, in which case lenalidomide should be permanently discontinued though patients will be followed for resolution of toxicity and for survival. In the event of a blistering skin rash the patient should have an urgent dermatology referral if grade 1 or 2 and should be hospitalized if grade 3 or 4. If a patient develops venous thromboembolism and/or pulmonary embolism while on therapeutic anticoagulation lenalidomide treatment should be permanently discontinued regardless of grade unless anticoagulation dosing was low (e.g., INR or anti-factor Xa was not in the generally accepted therapeutic range). Patients experiencing a venous thromboembolic event while on aspirin alone may stay on protocol at the discretion of the treating physician as long as the patient is subsequently on systemic anticoagulation with warfarin, low molecular weight heparin or equivalent for the duration of the study and as clinically indicated thereafter by the nature and extent of the thrombotic event. Patients experiencing an arterial thromboembolic event will be removed from study regardless of the anticoagulation status at the time of the event.

Per table 2, participants may be dose reduced if toxicities occur during cycle 1 at the starting dose of 10 mg daily. No more than 2 dose reductions will be permitted. If the participant cannot tolerate therapy after 2 dose reductions they should be permanently removed from the protocol.

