Grade 3 neutropenia associated with fever (temperature ≥ 38.5° C) or Grade 4 neutropenia	 Hold (interrupt) lenalidomide dose. Follow CBC weekly. If neutropenia has resolved to ≤ grade 2 prior to Day 21 of the current cycle, restart lenalidomide at next lower dose level and continue through the scheduled Day 21 of the current cycle. Otherwise, omit for remainder of cycle and reduce the dose of lenalidomide by 1 dose level at the start of the next cycle. Omitted doses are not made up. If neutropenia is the only toxicity for which a dose reduction is required, G-CSF may be used and the lenalidomide dose maintained.
Thrombocytopenia ≥Grade 3 (platelet count < 50,000/mm³)	 Hold (interrupt) lenalidomide dose. Follow CBC weekly. If thrombocytopenia resolves to ≤ grade 2 prior to Day 21 of the current cycle, restart lenalidomide at next lower dose level and continue through the scheduled Day 21 of the current cycle. Otherwise, omit for remainder of cycle and reduce the dose of lenalidomide by 1 dose level at the start of the next cycle. Omitted doses are not made up.
Platelet count < 50,000/mm ³	 Hold prophylactic anti-coagulation, if applicable. Restart prophylactic anti-coagulation when platelet count is ≥ 50,000/mm³.
Non-blistering rash Grade 3 Grade 4	 If Grade 3, hold (interrupt) lenalidomide dose. Follow weekly. If the toxicity resolves to ≤ grade 1 prior to Day 21 of the current cycle, restart lenalidomide at next lower dose level and continue through the scheduled Day 21 of the current cycle. Otherwise, omit for remainder of cycle and reduce the dose of lenalidomide by 1 dose level at the start of the next cycle. Omitted doses are not made up.
	• If Grade 4, discontinue lenalidomide. Remove patient from study.

Table 3: Dose Modifica	ations
NCI CTC Toxicity Grade	Dose Modification Instructions
Desquamating (blistering) rash- any Grade	• Discontinue lenalidomide. Remove patient from study. Immediate referral to dermatology and/or hospitalization if deemed clinically appropriate.
Neuropathy Grade 3	 If Grade 3, hold (interrupt) lenalidomide dose. Follow at least weekly. If the toxicity resolves to ≤ grade 1 prior to Day 21 of the current cycle, restart lenalidomide at next lower dose level and continue through the scheduled Day 21 of the current cycle. Otherwise, omit for remainder of cycle

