Grade 4	 and reduce the dose of lenalidomide by 1 dose level at the start of the next cycle. Omitted doses are not made up. If Grade 4, discontinue lenalidomide. Remove patient from study.
Venous thrombosis/embolism ≥ Grade 3	 Hold (interrupt) lenalidomide and start therapeutic anticoagulation, if appropriate. If VTE occurs while patient is on therapeutic anti-coagulation (not counting aspirin) permanently discontinue treatment. Restart lenalidomide at investigator's discretion (maintain dose level). See Anticoagulation Consideration (Section 5.6.1.2)
Hyperthyroidism or hypothyroidism	 Omit lenalidomide for remainder of cycle, evaluate etiology, and initiate appropriate therapy. See Instructions for Initiation of a New Cycle and reduce the dose of lenalidomide by 1 dose level.
Other non- hematologic toxicity ≥ Grade 3	 Hold (interrupt) lenalidomide dose. Follow at least weekly. If the toxicity resolves to ≤ grade 2 prior to Day 21 of the current cycle, restart lenalidomide and continue through the scheduled Day 21 of the current cycle. Otherwise, omit for remainder of cycle. Omitted doses are not made up. For toxicity attributed to lenalidomide, reduce the lenalidomide dose by 1 dose level when restarting lenalidomide.

Table 4. Tumor Flare Reaction Treatment (TFR)

Treatment of TFR is up to the discretion of the investigator, depending upon the severity and clinical situation. It is suggested that Grades 1 and 2 TFR be treated with NSAIDs (i.e., ibuprofen 400 to 600 mg orally every 4 to 6 hours as needed), corticosteroids, and/or narcotic analgesics for pain management.

In mild to moderate (Grades 1 and 2) cases, it is suggested that study drug be continued along with symptomatic treatment as above. In more severe cases, study drug should be interrupted.

Tumor Flare Reaction (TFR) ^a Grades 1-2	 Continue lenalidomide, maintain dose level At the investigator's discretion may initiate therapy with NSAIDs, limited duration corticosteroids, and/or narcotics
Grades 3-4	 Hold (interrupt dose) and initiate therapy with NSAIDs, corticosteroids, and/or narcotics When symptoms resolve to ≤ Grade 1, restart at same dose level for the rest of the Cycle

Treatment of Overdose

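### Section 6 and Table 3 take patients off study, not only off therapy, for four toxicities; read literally, this ends progression and survival follow-up and contradicts other sections

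*Combined protocol and SAP*

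**What the plan says.** The protocol defines two exits. Section 5.5 lists reasons to stop protocol therapy, and unacceptable adverse events are among them. Section 5.7 ("Participants will be removed from study when any of the following criteria apply") lists five reasons to leave the study: loss to follow-up, withdrawal of consent for data, subsequent therapy, death, and completion. None is a toxicity.

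Section 5.6 sets follow-up at three years from the start of treatment, "until subsequent therapy or until removal from study or death, whichever occurs first". It adds: "Participants removed from protocol therapy for unacceptable adverse event(s) will be followed until resolution or stabilization of the adverse event".

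Four toxicities in Section 6 are nevertheless worded as exits from the study:

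- Arterial thromboembolic event (text): "Patients experiencing an arterial thromboembolic event will be removed from study regardless of the anticoagulation status at the time of the event".
- Blistering rash, any grade (Table 3): "Discontinue lenalidomide. Remove patient from study. Immediate referral to dermatology".
- Non-blistering rash, grade 4 (Table 3): "If Grade 4, discontinue lenalidomide. Remove patient from study".
- Neuropathy, grade 4 (Table 3): the same instruction.

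For blistering rash the Section 6 text says something else: "lenalidomide should be permanently discontinued though patients will be followed for resolution of toxicity and for survival". Section 1 follows patients for 36 months or until a new therapy starts, with no exit for toxicity.

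**The concern.** A site has to know whether a patient stopped for one of these toxicities still gets disease assessments and survival follow-up. For blistering rash it is given two opposing instructions. For the other three, the instruction where the event is managed disagrees with the sections that define the exits.

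The endpoints at stake are PFS, OS and duration of response. Section 11.1.4 censors PFS at the last disease evaluation and OS at the date last known alive. Section 11.1.3 censors duration of response at the last disease evaluation. If follow-up stops because of a serious drug toxicity, the reason for censoring is related to treatment and may be related to prognosis. Later progressions or deaths in those patients would not be counted.

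**Working it through.** **1. The texts side by side**

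| Event | Section 6 text | Table 3 | Sections 5.5 and 5.7 |
|---|---|---|---|
| Blistering rash, any grade | drug stopped, survival followed | off study | off therapy only |
| Arterial event | off study | no row | off therapy only |
| Grade 4 non-blistering rash | not separately addressed | off study | off therapy only |
| Grade 4 neuropathy | not separately addressed | off study | off therapy only |

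The first row is an explicit contradiction. The others are inconsistent with the lists in 5.5 and 5.7. Adverse event follow-up under 5.6 runs to resolution or stabilization, and Section 7.3 collects SAEs for 30 days after the last dose. Neither covers progression or survival to month 36.

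**2. Most follow-up that could be lost**

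Inputs: 12 cycles of 28 days with dosing to day 21 (5.1); 36 months of follow-up (1, 5.6); 30.4375 days per month.

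- Last possible dosing day without delays: 11 × 28 + 21 = Day 329, and 329 / 30.4375 = 10.8 months.
- Event on the last dosing day: 36 − 10.8 = 25.2 months lost (70%).
- Event on Day 1: about 36 months lost.

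These are upper bounds, because Sections 1, 5.6 and 5.7 end follow-up at subsequent therapy under either wording.

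**3. Worst-case illustration for OS**

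Assume n = 12 (13.2). Of these, r patients are removed before any death and later die before month 36 without new therapy; d others die; everyone else is followed to month 36. If all are followed, OS = (12 − r − d)/12. If the r patients are censored at removal, OS = (12 − r − d)/(12 − r).

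| r | d | Followed | Censored | Gap (points) |
|---|---|---|---|---|
| 1 | 0 | 11/12 = 91.7% | 11/11 = 100% | 8.3 |
| 1 | 3 | 8/12 = 66.7% | 8/11 = 72.7% | 6.1 |
| 1 | 6 | 5/12 = 41.7% | 5/11 = 45.5% | 3.8 |
| 2 | 0 | 10/12 = 83.3% | 10/10 = 100% | 16.7 |
| 2 | 3 | 7/12 = 58.3% | 7/10 = 70.0% | 11.7 |
| 2 | 6 | 4/12 = 33.3% | 4/10 = 40.0% | 6.7 |

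**4. How often it could arise**

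The documents give no rate. For an assumed combined risk q per patient, the chance that at least one of 12 is affected is 1 − (1 − q)^12. This is 22%, 46%, 72% and 93% for q = 2%, 5%, 10% and 20%.

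**5. Primary endpoint**

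The exact 90% limits for 3/12 are 7.2% to 52.7%, which reproduces the 7-53% in Section 13.1. They do not depend on the off-study wording. Sections 11.1 and 13.7.2 keep every patient who takes one dose in the response assessment, so the denominator stays the same.

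Only confirmation of a response could be touched. A response first seen at C3D1 (2 × 28 + 1 = Day 57) must hold for 8 weeks (11.1.2.3), to Day 113. If dosing stops in cycle 3 or 4, the last dose is by 3 × 28 + 21 = Day 105. The off-treatment visit is then due by Day 112, one day short at nominal dates, and the next scan is the 3-month follow-up scan. The one-week scan window can close that gap: a first scan at Day 50 needs confirmation only from Day 106.

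**The case against.** The strongest reply is that *study* here is loose wording for *therapy*. Section 5.5 makes adverse events an off-therapy reason, 5.7 omits toxicity, and 5.6 describes adverse event patients as removed from protocol therapy. Calendar footnote c in Section 10 speaks of participants leaving the study for progressive disease, although progression is an off-therapy criterion in 5.5 and is absent from 5.7. One form also serves both exits. This is persuasive as to intent. It does not remove the contradiction for blistering rash, and it shows that the same slip occurs in a further place.

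The reply on size also largely stands. A patient with relapsed disease who loses the study drug may soon start another treatment and leave follow-up anyway. Section 13.6 specifies no 36-month OS estimate, and 13.2 anticipates a total duration of only 2.5 to 3 years.

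Three stronger readings are tempting, and the documents do not support them:

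- A reader might infer that PFS and OS will look better than they are. That requires removed patients to fare worse than the rest, which the documents do not show.
- A reader might infer that the decision rule of three responses is at risk. That needs a first response at C3D1, one of the four toxicities in cycle 3 or 4, exactly 3 of 12 responders, and a post-therapy scan being allowed to confirm. Section 13.5 counts best response during study therapy and does not settle the last condition.
- A reader might see a conflict with the venous event row: "If VTE occurs while patient is on therapeutic anti-coagulation (not counting aspirin) permanently discontinue treatment". Different toxicities may have different rules, so this is not one.

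**Conclusion.** The point holds as an inconsistency that should be corrected. The instructions are contradictory for blistering rash. For arterial events, grade 4 non-blistering rash and grade 4 neuropathy they are inconsistent with Sections 1, 5.5 and 5.7. Applied literally, they would stop progression and survival follow-up after serious drug toxicity and censor three secondary endpoints for a reason that may be informative.

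The loss is at most about 25 to 36 months per affected patient. The OS gaps of 3.8 to 16.7 points are worst cases that assume early removal, a later death before month 36 and no intervening therapy. The number of patients affected cannot be estimated from the documents. The primary denominator and the rule of three responses in 12 are unchanged, and any effect on confirming a response is conditional.

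**What to change.** In the arterial event sentence and the three Table 3 rows, replace removal from study with: *permanently discontinue lenalidomide; remove from protocol therapy; follow-up for response, progression and survival continues per 5.6*. Add a Table 3 row with the same instruction for arterial thromboembolic events. In calendar footnote c, change the wording on progressive disease to removal from protocol therapy. Keep 5.7 as the only off-study list.

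If the sponsor does intend off-study removal for these toxicities, it should add them to 5.7, change the blistering rash sentence, and state in 13.6 how such patients enter PFS, OS and response.

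The cost is a few words, one new row, and follow-up that the calendar already schedules for the few patients affected. Sample size and the primary analysis do not change.

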Grade 3 neutropenia associated with fever (temperature ≥ 38.5° C) or Grade 4 neutropenia	 Hold (interrupt) lenalidomide dose. Follow CBC weekly. If neutropenia has resolved to ≤ grade 2 prior to Day 21 of the current cycle, restart lenalidomide at next lower dose level and continue through the scheduled Day 21 of the current cycle. Otherwise, omit for remainder of cycle and reduce the dose of lenalidomide by 1 dose level at the start of the next cycle. Omitted doses are not made up. If neutropenia is the only toxicity for which a dose reduction is required, G-CSF may be used and the lenalidomide dose maintained.
Thrombocytopenia ≥Grade 3 (platelet count < 50,000/mm³)	 Hold (interrupt) lenalidomide dose. Follow CBC weekly. If thrombocytopenia resolves to ≤ grade 2 prior to Day 21 of the current cycle, restart lenalidomide at next lower dose level and continue through the scheduled Day 21 of the current cycle. Otherwise, omit for remainder of cycle and reduce the dose of lenalidomide by 1 dose level at the start of the next cycle. Omitted doses are not made up.
Platelet count < 50,000/mm ³	 Hold prophylactic anti-coagulation, if applicable. Restart prophylactic anti-coagulation when platelet count is ≥ 50,000/mm³.
Non-blistering rash Grade 3 Grade 4	 If Grade 3, hold (interrupt) lenalidomide dose. Follow weekly. If the toxicity resolves to ≤ grade 1 prior to Day 21 of the current cycle, restart lenalidomide at next lower dose level and continue through the scheduled Day 21 of the current cycle. Otherwise, omit for remainder of cycle and reduce the dose of lenalidomide by 1 dose level at the start of the next cycle. Omitted doses are not made up.
	• If Grade 4, discontinue lenalidomide. Remove patient from study.

Table 3: Dose Modifica	ations
NCI CTC Toxicity Grade	Dose Modification Instructions
Desquamating (blistering) rash- any Grade	• Discontinue lenalidomide. Remove patient from study. Immediate referral to dermatology and/or hospitalization if deemed clinically appropriate.
Neuropathy Grade 3	 If Grade 3, hold (interrupt) lenalidomide dose. Follow at least weekly. If the toxicity resolves to ≤ grade 1 prior to Day 21 of the current cycle, restart lenalidomide at next lower dose level and continue through the scheduled Day 21 of the current cycle. Otherwise, omit for remainder of cycle
Grade 4	 and reduce the dose of lenalidomide by 1 dose level at the start of the next cycle. Omitted doses are not made up. If Grade 4, discontinue lenalidomide. Remove patient from study.
Venous thrombosis/embolism ≥ Grade 3	 Hold (interrupt) lenalidomide and start therapeutic anticoagulation, if appropriate. If VTE occurs while patient is on therapeutic anti-coagulation (not counting aspirin) permanently discontinue treatment. Restart lenalidomide at investigator's discretion (maintain dose level). See Anticoagulation Consideration (Section 5.6.1.2)
Hyperthyroidism or hypothyroidism	 Omit lenalidomide for remainder of cycle, evaluate etiology, and initiate appropriate therapy. See Instructions for Initiation of a New Cycle and reduce the dose of lenalidomide by 1 dose level.
Other non- hematologic toxicity ≥ Grade 3	 Hold (interrupt) lenalidomide dose. Follow at least weekly. If the toxicity resolves to ≤ grade 2 prior to Day 21 of the current cycle, restart lenalidomide and continue through the scheduled Day 21 of the current cycle. Otherwise, omit for remainder of cycle. Omitted doses are not made up. For toxicity attributed to lenalidomide, reduce the lenalidomide dose by 1 dose level when restarting lenalidomide.

Table 4. Tumor Flare Reaction Treatment (TFR)

Treatment of TFR is up to the discretion of the investigator, depending upon the severity and clinical situation. It is suggested that Grades 1 and 2 TFR be treated with NSAIDs (i.e., ibuprofen 400 to 600 mg orally every 4 to 6 hours as needed), corticosteroids, and/or narcotic analgesics for pain management.

In mild to moderate (Grades 1 and 2) cases, it is suggested that study drug be continued along with symptomatic treatment as above. In more severe cases, study drug should be interrupted.

Tumor Flare Reaction (TFR) ^a Grades 1-2	 Continue lenalidomide, maintain dose level At the investigator's discretion may initiate therapy with NSAIDs, limited duration corticosteroids, and/or narcotics
Grades 3-4	 Hold (interrupt dose) and initiate therapy with NSAIDs, corticosteroids, and/or narcotics When symptoms resolve to ≤ Grade 1, restart at same dose level for the rest of the Cycle

Treatment of Overdose

In the case of overdose, clinic staff should be notified immediately and supportive care is to be given as indicated. Patients should be informed to contact their doctor immediately if they have taken an overdose and should stop taking lenalidomide. There is no known antidote for lenalidomide.

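### Section 6 and its Table 3 take patients off study, not just off treatment, for certain toxicities, in conflict with the section 6 text on blistering rash and with sections 5.5 and 5.7

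*Combined protocol and SAP*

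**What the plan says.** Section 6 ends study participation for four kinds of toxicity:

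- Blistering rash, any grade (Table 3, Dose Modifications): "Discontinue lenalidomide. Remove patient from study. Immediate referral to dermatology and/or hospitalization if deemed clinically appropriate".
- Non-blistering rash, grade 4 (Table 3): "If Grade 4, discontinue lenalidomide. Remove patient from study".
- Neuropathy, grade 4 (Table 3): again, "discontinue lenalidomide. Remove patient from study".
- Arterial events (section 6 text): "Patients experiencing an arterial thromboembolic event will be removed from study regardless of the anticoagulation status at the time of the event".

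For blistering rash the section 6 text says something different: "lenalidomide should be permanently discontinued though patients will be followed for resolution of toxicity and for survival".

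Section 5.5 makes an unacceptable adverse event a reason to stop protocol therapy. Section 5.7, which opens "Participants will be removed from study when any of the following criteria apply", lists five reasons: loss to follow-up, withdrawal of consent to data submission, start of a later therapy, death, and completion of study procedures. Toxicity is not among them. Section 5.6 plans three years of follow-up, cut short by later therapy, removal from study, or death.

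**The concern.** Leaving treatment and leaving the study are different events, and sections 5.5 and 5.7 define them separately. Section 6 uses the second where 5.5 would place the first. Under 5.6 the choice of word matters, because removal from study ends follow-up while removal from protocol therapy does not.

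Applied literally, section 6 would take patients out of PFS, OS and duration-of-response follow-up at the moment of a serious toxicity. If their prognosis differs from that of the remaining patients, the censoring is informative. A response seen shortly before removal might also lack the later scan needed to show that it was maintained.

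**Working it through.** **1. The conflicts, event by event**

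| Event | Off-study instruction | Conflicts with |
|---|---|---|
| Blistering rash, any grade | Table 3 | Section 6 text (toxicity and survival follow-up continue); 5.5; 5.7 |
| Grade 4 non-blistering rash | Table 3 | 5.5; 5.7 |
| Grade 4 neuropathy | Table 3 | 5.5; 5.7 |
| Arterial thromboembolism | Section 6 text | 5.5; 5.7 |

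Section 1 also plans 36 months of follow-up or until a new therapy, with no exception for toxicity. Section 5.2.2 shows that the protocol can make the distinction: there, unresolved toxicity removes the participant from treatment.

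**2. What follows for PFS and OS**

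Removal from study ends follow-up (5.6). A patient without an event is then censored for PFS at the last disease evaluation and for OS at the date last known alive (11.1.4), or at last contact for both (13.6). No sensitivity analysis addresses this censoring.

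**3. What follows for response**

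Responses should be maintained for at least 8 weeks (11.1.2.3). With 28-day cycles, C3D1 falls at (3 − 1) × 4 = 8 weeks and C6D1 at (6 − 1) × 4 = 20 weeks, so the scans are 12 weeks apart. The off-treatment scan is due within 7 days of the last dose. If a patient responds at C3D1 and stops soon afterwards, that scan can fall less than 8 weeks after the response. The next scan is at the follow-up visit 3 months after the last dose, which takes place only if the patient is still on study.

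**4. The plan's own figures (13.1)**

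The exact 90% limits for 3 of 12 come out at 7.2% to 52.7%, matching the stated 7-53%. For 2 of 12 they are 3.0% to 43.8%, which includes 5%, as stated. The chance of at least 3 responses at a true rate of 5% is 1 − Σ C(12, x) 0.05^x 0.95^(12−x), summed over x = 0 to 2, which is 0.0196. None of these depends on the off-study wording. No event target, power or hypothesis is given for PFS or OS.

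**5. Illustration of size (assumptions, not document figures)**

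Let a share f be removed early, with event risk q1 in those removed and q0 in the others. Kaplan-Meier then estimates 1 − q0. The true value is 1 − [(1 − f)q0 + f·q1]. The overstatement is f(q1 − q0).

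Take q0 = 0.30. This is close to the 28-32% deaths that section 2.1 reports for adult LCH, but over 4 to 6.5 years, so it is only a round value here.

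| q1 | f = 1/12 | f = 2/12 | f = 3/12 |
|---|---|---|---|
| 0 | −2.5 points | −5.0 | −7.5 |
| 0.30 | 0 | 0 | 0 |
| 0.60 | +2.5 | +5.0 | +7.5 |
| 0.90 | +5.0 | +10.0 | +15.0 |

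In actual counts, suppose k patients are removed before any death and 3 deaths occur among the rest. The Kaplan-Meier value is 1 − 3/(12 − k). The value with full follow-up lies between (9 − k)/12 and 9/12.

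- k = 1: 72.7%, against 66.7% to 75.0%
- k = 2: 70.0%, against 58.3% to 75.0%
- k = 3: 66.7%, against 50.0% to 75.0%

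**The case against.** The strongest reply is that sections 5.5 and 5.7 are the operative rules, that sites would follow them, and that the Table 3 wording is loose drafting. Follow-up visits are already in the calendar, and PFS and OS are descriptive secondary endpoints in a 12-patient pilot whose only decision rule concerns response. All of that limits the consequence. It does not remove the contradiction, because 5.6 itself names removal from study as an end of follow-up.

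A reader might go further than the documents allow in four ways:

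- *That survival follow-up is promised for all four events.* The section 6 text promises it for blistering rash only. The other three conflict with 5.5 and 5.7.
- *That PFS and OS would certainly be biased upward.* That needs literal application and a worse prognosis in the removed patients. The documents show neither, and equal risk gives no bias.
- *That a patient removed before C3D1 has no response scan.* The calendar marks tumor measurements and radiology at the off-treatment visit, which is timed from the last dose.
- *That late safety data are generally lost.* SAE reporting runs to 30 days after the last dose (7.3.1), and 5.6 follows adverse events to resolution or stabilization after removal from protocol therapy for toxicity. What stands is that 5.6 does not say whether this covers a patient removed from study.

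The documents also give no incidence for the four events in this population, and section 2.1 states that lenalidomide does not cause neuropathy. The range of 1 to 3 patients is therefore purely illustrative.

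**Conclusion.** The inconsistency is certain; its effect on the estimates is conditional. There is one direct contradiction (blistering rash) and three further events whose off-study wording does not fit 5.5 and 5.7. If the wording is followed literally, each such patient, 1/12 or about 8% of the sample, is censored for PFS and OS at a serious toxicity. Direction and size of any bias cannot be determined from the documents.

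The primary analysis is affected only at its edge. Every dosed patient stays in the response denominator (11.1, 13.7.2), but a response could fail to be documented as maintained. With a threshold of 3 of 12, one such case matters only if the count would otherwise be exactly 3. Section 13.5 counts best response during study therapy and does not say whether maintenance may be shown after therapy ends, so this effect is possible rather than established.

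This should be corrected before the time-to-event data are collected under conflicting instructions.

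**What to change.** Reconcile the section 6 text, Table 3, 5.6 and 5.7. Where one of these four events ends treatment, record it as removal from protocol therapy, and state that disease assessment and survival follow-up continue under 5.6 and the study calendar. Say the same in 11.1.4 and 13.6, so that the censoring date for such patients is unambiguous. At the same time, clarify the sentences in section 6 that take patients off the protocol when they cannot tolerate the last permitted dose reduction; they leave the same question open.

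The rules for when lenalidomide is stopped stay as they are; the change concerns only data collection afterwards. The cost is wording, since the off-treatment and follow-up visits are already scheduled. The change does not deal with the separate rule in 5.6 and 5.7 that ends follow-up when a later therapy begins, which can also censor OS for a reason related to outcome.
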